3.3.4 Dose adjustments for Non hematologic toxicity

Lenalidomide Common Non-hematologic Toxicities	Dose Modifications
Non Blistering Rash	If Grade 3, hold lenalidomide, and restart at next lower dose level once rash improves to ≤ Grade 2.
Blistering, exfoliative or bullous rash (any grade), or suspected Stevens Johnson Syndrome (SJS) or Toxic Epidermal Necrolysis (TEN)	Discontinue lenalidomide and remove patient from therapy.
Venous or arterial thrombosis/embolism	Hold lenalidomide and start therapeutic anticoagulation. Restart lenalidomide at investigator's discretion at current or reduced dose level. Patient should continue anticoagulation therapy during the course of lenalidomide treatment. Additional work up to determine the cause of thromboembolic events may be done as clinically indicated at the discretion of investigator.
Renal Dysfunction CrCl based on Cockcroft-Gault formula: CrCl = (140 – Age) x Mass (in kilograms) x [0.85 if Female] 72 x Serum Creatinine (in mg/dL)	
 CrCl 31-60 ml/min – no dose modifications CrCl ≤30 mL/min (not requiring dialysis) – Dose reduce Lenalidomide to 10 mg every 48 hours CrCl ≤30 mL/min (requiring dialysis) – Decrease Lenalidomide to 5 mg daily and on dialysis days, dose lenalidomide after dialysis.
Other non-hematologic grade 3/4 toxicities judged to be related to lenalidomide. Readily reversible electrolyte and metabolic abnormalities or infections controlled by appropriate therapy are exempt.	Hold treatment and restart at next lower dose level when toxicity has resolved to ≤Grade 2

3.3.5 Monitoring (see study calendar for more specific details) Please Note: Day 1 may be delayed for up to one week for Cycle 2 and beyond.

3.3.5.1 Routine labs (CBC with diff, retic count, acute care panel, mineral panel, hepatic panel, LDH, uric acid) will be performed on Day 1 (within 3 days prior) and Day 15

Abbreviated Title: Revlimid maintenance for MM

Version Date: 01/06/2017

(within 3 days prior) of first cycle, on Day 1 (within 3 days prior) of cycles 2, 4 and 7 and on Day 1 (within 3 days prior) of every third cycle starting at cycle 10 at scheduled clinic visits, at the time of documented CR, and at disease progression (see study calendar).

- 3.3.5.2 Random urine sample for protein electrophoresis (UPEP) and immunofixation to assess for monoclonal protein in the urine (Bence-Jones proteinuria) will be performed at baseline, on Day 1 (within 3 days prior) of cycles 2, 4 and 7 and on Day 1 (within 3 days prior) of every third cycle starting at cycle 10 at scheduled clinic visits, at the time of documented CR, and at disease progression (see study calendar).
- 3.3.5.3 Myeloma tests including serum protein electrophoresis, serum immunofixation, serum free light chains, quantitative immunoglobulins, beta-2 microglobulin will be performed at baseline, on Day 1 (within 3 days prior) of cycles 2, 4 and 7 and on Day 1 (within 3 days prior) of every third cycle starting at cycle 10 at scheduled clinic visits, at the time of documented CR, and at disease progression (see study calendar).
- 3.3.5.4 Patients will have clinic visits with H&P or standard progress notes assessing for toxicity/side effects on Day 1 (within 3 days prior), and 15 (within 3 days prior) of cycle 1 and Day 1 (within 3 days prior) of cycles 2, 4 and 7 and on Day 1 (within 3 days prior) of every third cycle starting at cycle 10 at scheduled clinic visits (see study calendar).
- 3.3.5.5 Skeletal survey to assess disease status will be performed at baseline. The skeletal survey at the time of documented CR or disease progression is optional.
- 3.3.5.6 Evaluation of bone marrow for disease status will be performed at baseline, and then at the time of documented CR or disease progression. Additional bone marrow samples to evaluate disease status, treatment effect, or biomarker studies will be obtained at the discretion of PI, if patients are willing.
- 3.3.5.7 Additional laboratory studies and clinic visits may be performed as clinically indicated.
- 3.3.5.8 Patients removed from protocol therapy for unacceptable adverse events will be followed until resolution or stabilization of the adverse event. Further follow-up can be assessed either by phone consultation or clinic appointment at the discretion of the PI.

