3.5 CRITERIA FOR REMOVAL FROM PROTOCOL THERAPY AND OFF STUDY CRITERIA

3.5.1 Criteria for removal from protocol therapy

- 3.5.1.1 Patients with medically concerning grade 3 or 4 adverse events related to study drug may be taken off therapy at the discretion of the principal investigator.
- 3.5.1.2 Toxicity has not resolved after 8 weeks of withholding treatment
- 3.5.1.3 Grade 4 non-blistering rash, or blistering rash of any grade
- 3.5.1.4 Grade 4 neuropathy
- 3.5.1.5 Grade 4 hypersensitivity reaction
- 3.5.1.6 Progression of disease
- 3.5.1.7 Patient chooses to go off therapy
- 3.5.1.8 The principal investigator may remove patient from protocol therapy if deemed necessary due to medical conditions, compliance, etc.
- 3.5.1.9 Diagnosis of new malignancy
- 3.5.1.10 Patient becomes pregnant.

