11.1.2 Toxicity

Fetal Risk

Do not use REVIMID during pregnancy. Lenalidomide, a thalidomide analogue, caused limb abnormalities in a developmental monkey study. Thalidomide is a known human teratogen that causes severe life-threatening human birth defects. If lenalidomide is used during pregnancy, it may cause birth defects or death to a developing baby. In women of childbearing potential, obtain 2 negative pregnancy tests before starting REVIMID® treatment. Women of childbearing potential must use 2 forms of contraception or continuously abstain from heterosexual sex during and for 4 weeks after REVIMID treatment

Hematologic Toxicity

REVIMID can cause significant neutropenia and thrombocytopenia.

In the pooled MM studies Grade 3 and 4 hematologic toxicities were more frequent in patients treated with the combination of REVIMID and dexamethasone than in patients treated with dexamethasone alone

Deep Vein Thrombosis and Pulmonary Embolism

Venous thromboembolic events (predominantly deep venous thrombosis and pulmonary embolism) have occurred in patients with MM treated with lenalidomide combination therapy. A significantly increased risk of DVT and PE was observed in patients with MM who were treated with REVIMID and dexamethasone therapy in a clinical trial.

Allergic Reactions

Angioedema and serious dermatologic reactions including Stevens-Johnson syndrome (SJS) and toxic epidermal necrolysis (TEN) have been reported. These events can be fatal. Patients with a prior history of Grade 4 rash associated with thalidomide treatment should not receive REVIMID. REVIMID interruption or discontinuation should be considered for Grade 2-3 skin rash. REVIMID must be discontinued for angioedema, Grade 4 rash, exfoliative or bullous rash, or if SJS or TEN is suspected and should not be resumed following discontinuation for these reactions.

Tumor Lysis Syndrome

Fatal instances of tumor lysis syndrome have been reported during treatment with lenalidomide. The patients at risk of tumor lysis syndrome are those with high tumor burden prior to treatment. These patients should be monitored closely and appropriate precautions taken.

Most common adverse reactions (>20%)

Fatigue, neutropenia, constipation, diarrhea, muscle cramp, anemia, pyrexia, peripheral edema, nausea, back pain, upper respiratory tract infection, dyspnea, dizziness, thrombocytopenia, tremor and rash

Abbreviated Title: Revlimid maintenance for MM
Version Date: 01/06/2017

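### The dosing table in 3.3.4 directs a restart after related Grade 3 angioedema, which 11.1.2 forbids, and 3.5.1 does not make removal mandatory

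*Combined protocol and SAP*

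**What the plan says.** Three places in the protocol bear on this.

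- **Section 3.3.4, last row.** The trigger is "Other non-hematologic grade 3/4 toxicities judged to be related to lenalidomide". The action is "Hold treatment and restart at next lower dose level when toxicity has resolved to ≤Grade 2". There are two exemptions: "Readily reversible electrolyte and metabolic abnormalities or infections controlled by appropriate therapy are exempt". Another row, for blistering, exfoliative or bullous rash and suspected SJS or TEN, says "Discontinue lenalidomide and remove patient from therapy"; angioedema is not in it.
- **Section 11.1.2, Allergic Reactions.** Lenalidomide "must be discontinued for angioedema, Grade 4 rash, exfoliative or bullous rash, or if SJS or TEN is suspected and should not be resumed" after these reactions. Of angioedema and the serious skin reactions it says "These events can be fatal".
- **Section 3.5.1, removal from therapy.** Ten criteria, none naming angioedema. Patients with medically concerning related Grade 3 or 4 events "may be taken off therapy at the discretion of the principal investigator" (3.5.1.1). Criterion 3.5.1.2 reads "Toxicity has not resolved after 8 weeks of withholding treatment". Criterion 3.5.1.5 covers hypersensitivity reactions at Grade 4 only.

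**The concern.** Section 3.3.4 is where an investigator looks when deciding whether and how to re-dose. For a related Grade 3 angioedema it leads to a restart one level down, while the drug section of the same protocol requires permanent discontinuation. The restart condition also allows dosing to resume while Grade 1 or 2 angioedema is still present. An investigator who restarts complies with 3.3.4 and contradicts 11.1.2. What is at stake is the safety of the individual patient; no endpoint, power or sample size figure is touched.

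**Working it through.** No arithmetic applies, so the check is a comparison of the texts.

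**1. Which row of 3.3.4 applies?** The table has 5 rows: non-blistering rash; blistering, exfoliative or bullous rash with suspected SJS or TEN; thrombosis or embolism; renal dysfunction; and the residual row. Angioedema is named in 0 of 5. A related Grade 3 case therefore meets the residual row, and neither exemption (electrolyte or metabolic abnormalities, controlled infections) fits it.

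**2. What restart does that give?** By the dose steps in 3.3.1, a patient on 10 mg restarts at 5 mg, and a patient on 5 mg restarts at 5 mg every other day.

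**3. Does 3.5.1 override the restart?** Take a related Grade 3 angioedema that falls to Grade 2 or less within 8 weeks:

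| Criterion | Mandatory removal because of this event? |
|---|---|
| 3.5.1.1 medically concerning related Grade 3/4 event | No, discretionary |
| 3.5.1.2 unresolved after 8 weeks of holding | No, the event has resolved |
| 3.5.1.3 rash | No, rash only |
| 3.5.1.4 neuropathy | No |
| 3.5.1.5 hypersensitivity | No, Grade 4 only |
| 3.5.1.6 progression | No |
| 3.5.1.7 patient's choice | No |
| 3.5.1.8 investigator's decision | No, discretionary |
| 3.5.1.9 new malignancy | No |
| 3.5.1.10 pregnancy | No |

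The count is 0 of 10.

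**4. Is this a choice or an omission?** The 11.1.2 sentence has 5 stop conditions:

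| Stop condition in 11.1.2 | Where section 3 carries it |
|---|---|
| Exfoliative or bullous rash | 3.3.4, discontinuation row |
| Suspected SJS | 3.3.4, discontinuation row |
| Suspected TEN | 3.3.4, discontinuation row |
| Grade 4 rash | 3.5.1.3 |
| Angioedema | Nowhere |

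Section 3 carries 4 of 5, and no rationale for rechallenge after angioedema appears in the protocol. This points to an omission.

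**5. Other grades.** At Grade 4, 3.5.1.5 probably removes the patient, because 11.1.2 lists angioedema among allergic reactions; the conflict reaches Grade 4 only if the event is not classed as hypersensitivity. At Grades 1 and 2 the residual row does not apply, so 11.1.2 stands alone: section 3 is silent there, without contradiction. Grade 4 neuropathy, Grade 4 hypersensitivity and Grade 4 non-blistering rash raise no issue, since 3.5.1.4, 3.5.1.5 and 3.5.1.3 already remove those patients.

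**The case against.** The strongest reply is that the protocol already contains the right answer. Section 11.1.2 names angioedema expressly, and a specific instruction would ordinarily prevail over a residual row in a table headed as covering common toxicities. An investigator can also act on it from within section 3: 3.5.1.1 and 3.5.1.8 permit removal, and treatment ends at unacceptable toxicity in any case. On that reading only a cross-reference is missing.

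There are real safeguards as well. Exclusion 2.1.2.20 bars patients with earlier severe adverse events or hypersensitivity to thalidomide or lenalidomide. Toxicity is evaluated before each cycle (3.3). Clinical Center physicians prescribe monthly, one cycle at a time (3.2), so a restart takes a deliberate act. The research team discusses each patient, and the principal investigator reviews adverse events (7.3.1). Harm requires a first on-study Grade 3 event and a prescriber who overlooks 11.1.2.

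Much of this stands, and it lowers the probability of harm. It does not remove the conflict. The protocol nowhere says that 11.1.2 takes precedence over 3.3.4. Permission to stop is weaker than the requirement to stop in 11.1.2. The exclusion looks backwards and does not cover a first reaction on study. From Cycle 4, drug can be sent by express delivery after phone counseling (3.2), and from Cycle 7 scheduled clinic visits fall every third cycle (3.3.5.4), so a restart need not coincide with an in-person visit. The residual row also lacks the clinical-judgment allowance found in the notes to the thrombocytopenia and neutropenia tables and in the thrombosis row.

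**Conclusion.** The concern holds. For a related Grade 3 angioedema that improves to Grade 2 or less within 8 weeks, 3.3.4 directs a restart, 3.5.1 offers only optional removal, and 11.1.2 requires permanent discontinuation. One event is affected: certainly at Grade 3 under those conditions, and at Grade 4 only if it is not classed under 3.5.1.5.

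The conclusion assumes that 11.1.2 means angioedema of any grade. Those words are not printed; the reading rests on the sentence grading rash but leaving angioedema ungraded. The documents give no rate for angioedema, so the number of patients affected among 28 cannot be estimated; it is likely to be small. The case for correcting it before use rests on the consequence of following the table, not on how often that would happen.

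**What to change.** Make three wording changes:

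1. In 3.3.4, add *angioedema (any grade)* to the row that now covers blistering, exfoliative or bullous rash and suspected SJS or TEN.
2. In 3.5.1, list angioedema as a criterion for removal from therapy.
3. In the residual row of 3.3.4, add *except events listed in 3.5.1 or requiring discontinuation under 11.1.2*.

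The first change removes the conflict in the table, and also fills the table's silence on Grades 1 and 2. The second brings the removal list into line. The third guards against similar gaps; for the Grade 4 events already in 3.5.1 it is only a clarification.

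The cost is a wording amendment to two rows of one table and one added list item, with no extra visits, tests or patients.

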3.4 STUDY CALENDAR

Study	Pre-treatment (Screening/ Baseline)	Maintenance Treatment until progression, unacceptable toxicity or completion of two years of lenalidomide therapy and the 30 day safety follow-up visit				CR achieved	Progressive disease	Follow up- off protocol therapy ^{l, m}	
		Cycle 1		Cycles 2, 4 and 7	Cycle 10 and beyond-every 3 cycles			Determine at PI's discretion	
		Day ^k 1	Day ^k 15	Day ^m 1	Day ^m 1			Any day	
Medical Record Review	x								x
H&P/clinic visit	x	x	x	x	x	x	x	x	
ECOG	x	x	x	x	x	x	x	x	
Informed Consent	x								
Routine Labs ^a	x	x	x	x	x	x	x	x	
Viral Studies ^b	x								
Register for REMS	x								
Pregnancy Test ^c	x ^c	x ^d	x ^e	x ^e	x ^e	x ^e			
Myeloma tests ^f	x			x	x	x	x	x	
Urine for UPEP and IFE ^g	x			x	x	x	x	x	
Bone marrow/aspirate ^h	x					x	x	x	
Blood for - biomarkers		x		x	x	x	x	x	
12 lead EKG	x								
Skeletal survey	x						x ^j	x ^j	
Adverse Events/Toxicity		x							→
Storage blood/urine		x		x	x	x	x	x	

Abbreviated Title: Revlimid maintenance for MM
Version Date: 01/06/2017

- a. Routine tests include CBC, reticulocyte count, acute care panel, mineral panel and hepatic panel, uric acid, LDH and calculated CrCl. PT and PTT will only be performed at baseline.
- b. Viral studies include: HIV, Hep B surface antigen and Hep C antibody. If Hep C antibody positive, Hep C RNA PCR will be performed.
- c. Pregnancy tests (urine or serum) for females of childbearing potential. A female of childbearing potential (FCBP) is a sexually mature female who: 1) has not undergone a hysterectomy or bilateral oophorectomy; or 2) has not been naturally postmenopausal for at least 24 consecutive months (i.e., has had menses at any time in the preceding 24 consecutive months)
- d. Pregnancy tests (urine or serum) must occur within 10 – 14 days and again within 24 hours prior to prescribing lenalidomide for Cycle 1 (prescriptions must be filled within 7 days).
- e. FCBP with regular or no menstruation must have a pregnancy test (serum or urine) weekly for the first 28 days and then every 28 days while on therapy (including breaks in therapy); at discontinuation of lenalidomide and at Day 28 post the last dose of lenalidomide. Females with irregular menstruation must have a pregnancy test (serum or urine) weekly for the first 28 days and then every 14 days while on therapy (including breaks in therapy), at discontinuation of lenalidomide and at Day 14 and Day 28 post the last dose of lenalidomide (see Appendix A: Risks of Fetal Exposure, Pregnancy Testing Guidelines and Acceptable Birth Control Methods).
- f. Myeloma tests include serum protein electrophoresis, serum immunofixation, , serum free light chains, quantitative immunoglobulins, and beta-2 microglobulin will be performed at baseline, on Day 1 (within 3 days prior) of Cycle 2, Cycle 4, and Cycle 7, and thereafter every 3 cycles, at the time of documented CR, and at disease progression.
- g. Random urine sample for protein electrophoresis (UPEP) and immunofixation to assess for monoclonal protein in the urine (Bence-Jones proteinuria) will be performed at baseline, on Day 1 (within 3 days prior) of Cycle 2, Cycle 4, and Cycle 7, and thereafter every 3 cycles, at the time of documented CR, and at disease progression.
- h. Bone marrow aspirate and biopsy can be performed +/- 21 days of intended cycle day. Bone marrow aspirate and biopsy will be sent to Hematology Service of the Department of Laboratory Medicine and Flow cytometry for immunophenotyping of plasma cells. CD 138 sorting/GEP/quantitative PCR/ storage will be done in Molecular pathology or Lymphoid Malignancies Branch lab... For questions regarding these samples, please contact [name] at [contact]. Effective with Amendment D, bone marrow aspirate and biopsy will be obtained for research studies at the discretion of the PI.
- i. Blood for biomarker analysis will be collected on D1 (within 3 days prior) of Cycle 1, Cycle 2, Cycle 4, Cycle 7 and every 6 cycles thereafter.
- j. Skeletal survey to assess disease status will be performed at baseline. The skeletal survey at the time of documented CR or disease progression is optional.
- k. Variations of +/- 3 days of scheduled visits are permitted.
- l. Patients removed from protocol therapy for unacceptable toxicities will be followed until resolution or stabilization of the adverse event. Further follow-up for patients taken off protocol therapy can be assessed either by phone consultation or clinic appointment at the discretion of the PI.
- m. Day 1 may be delayed for up to one week for Cycle 2 and beyond.

3.5 CRITERIA FOR REMOVAL FROM PROTOCOL THERAPY AND OFF STUDY CRITERIA

3.5.1 Criteria for removal from protocol therapy

- 3.5.1.1 Patients with medically concerning grade 3 or 4 adverse events related to study drug may be taken off therapy at the discretion of the principal investigator.
- 3.5.1.2 Toxicity has not resolved after 8 weeks of withholding treatment
- 3.5.1.3 Grade 4 non-blistering rash, or blistering rash of any grade
- 3.5.1.4 Grade 4 neuropathy
- 3.5.1.5 Grade 4 hypersensitivity reaction
- 3.5.1.6 Progression of disease
- 3.5.1.7 Patient chooses to go off therapy
- 3.5.1.8 The principal investigator may remove patient from protocol therapy if deemed necessary due to medical conditions, compliance, etc.
- 3.5.1.9 Diagnosis of new malignancy
- 3.5.1.10 Patient becomes pregnant.

3.5.2 Criteria for removal from study

- 3.5.2.1 Patient requests to be withdrawn from study
- 3.5.2.2 Death
- 3.5.2.3 Physician's determination that withdrawal is in the patient's best interest
- 3.5.2.4 Effective with amendment D, version date February 12, 2015, patients, will be removed from the study when they have completed two years of lenalidomide therapy and the 30 day safety follow-up visit. Patients who have on-going toxicity(ies) will be followed as described in Section **7.1.1**.

3.5.2.5 Study closure

3.5.3 Off Study Procedure

Authorized staff must notify Central Registration Office (CRO) when a subject is taken off-study. An off-study form from the web site (<http://home.ccr.cancer.gov/intra/eligibility/welcome.htm>) main page must be completed and faxed to [contact].

4 CONCOMITANT MEDICATIONS/MEASURES

4.1 TUMOR LYSIS SYNDROME

4.1.1 Allopurinol is optional and will be prescribed at the Investigator's discretion. Allopurinol dose should be adjusted according to the package insert. Subjects who do not tolerate allopurinol should be discussed with the Lead Principal Investigator.

4.2 BONE DISEASE/EXTRAMEDULLARY DISEASE

4.2.1 Subjects may receive radiation if clinically indicated for treatment of uncontrolled pain, cord compression, vertebral instability/impending fracture, etc, in the face of non progressive disease

4.2.2 Kyphoplasty/Vertebroplasty: Subjects may receive kyphoplasty/vertebroplasty for symptomatic vertebral compression fractures in the face of non progressive disease.

4.2.3 Bisphosphonate therapy: Approved bisphosphonate therapy (zoledronic acid or pamidronate) is allowed. Patients will be monitored for renal function and osteonecrosis of the jaw. Patients may require prior evaluation from dental specialist before instituting bisphosphonates.

4.3 USE OF STEROIDS

4.3.1 Use of corticosteroids during maintenance therapy with the intent to treat myeloma is not permitted. However, corticosteroids may be used as medically indicated for non-myeloma related acute indications e.g. to control symptoms of asthma flare. Corticosteroids should be discontinued as soon as possible.

4.4 HYPERCALCEMIA

4.4.1 Patients may receive treatment for hypercalcemia including hydration, bisphosphonates, furosemide, steroids, calcitonin, etc.

4.5 TRANSFUSIONS/GROWTH FACTORS

4.5.1 Subjects may receive RBC or platelet transfusions if clinically indicated.

4.5.2 Subjects may receive supportive care with erythropoietin or darbopoetin.

4.5.3 Prophylactic use of growth factors (i.e. filgrastim, pegfilgrastim) is not permitted. However, therapeutic use of filgrastim or sargramostim in patients with serious neutropenic conditions, such as sepsis, febrile neutropenia may be considered at the investigator's discretion. Colony-stimulating factors may be used if grade 4 neutropenia occurs but should not be given prophylactically.

4.6 ANTI-COAGULATION

4.6.1 Oral Aspirin 81 mg or 325 mg or suitable alternative anti-coagulation for thrombotic prophylaxis every day for the duration of their participation in the study.

4.7 ANTI-EMETICS

Abbreviated Title: Revlimid maintenance for MM

Version Date: 01/06/2017

4.7.1 Anti-emetics should not be given prophylactically. If a patient demonstrates the need for anti-emetics, their use will be at the treating physician's discretion.

4.8 PCP PROPHYLAXIS

4.8.1 The use of medication (e.g. Bactrim) for PCP prophylaxis is at the investigator's discretion.

